10.6.2.2 Secondary Efficacy Analyses

Secondary efficacy analyses will include:

- Typical use Life-Table estimate of the cumulative probability of pregnancy through 3 treatment cycles in the Treated Population (excluding women randomized to the upper arm)
- Pearl Index that excludes follow-up periods during which participants report using other contraceptives (including condoms), drugs known to impact ovarian function, or drugs known to impact the PK of MPA, unless she became pregnant in that period
- Pearl Index that includes any pregnancies with EDF that fall in an 8-28 day 'late' period for reinjections or final visits, as well as all person-time (regardless of pregnancy status) contributed to these periods
- Pearl Index computed per the primary analysis, but including women randomized to receive injections in the upper arm

In addition to the non-comparative analyses listed above, a Pearl Index will be computed separately by anatomical site of injection (abdomen or thigh), and the difference in pregnancy risk between site of injection will be assessed using a log-rank test, stratified on clinic site.

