Treatment assignments will be concealed within sealed, opaque, sequentially numbered randomization envelopes provided to each study center. Each envelope will have the randomization number printed on the outside, with the corresponding SC injection site assignment concealed within. The randomization envelopes will be maintained in a secure location at each study center, with access limited to authorized personnel per center-specific study procedures. Trained center staff will open the next available envelope (from the appropriate sequence of envelopes based on which cohort the participant consented to), and allocate the next treatment assignment, only after a participant has been confirmed to be eligible, consented to participate, and undergone all other enrollment procedures, including having a blood sample collected for MPA testing among women agreeing to participate in the PK cohort.

C. Blinding

Since this study is not randomizing study drug but rather site of SC injection, neither participants nor center staff will be blinded. However, laboratory staff analyzing serum MPA specimens and staff at FHI 360 responsible for adjudicating pregnancy outcomes and coding adverse events will be blinded to individual participant injection site assignments for the duration of each participant's follow up. Other FHI 360 staff may review interim PK data, including MPA concentrations of any women who become pregnant, to inform other FHI 360 MPA projects (see DSMB Operational Plan for details on timing of any un-blinded review of PK data).

² In September 2018, 100 of the planned enrollment total for UNICAMP, Brazil were shifted to Profamilia, DR due to study timelines and slower than expected enrollment at the UNICAMP center.

V. Analysis Populations and Analysis Sets

In the below definitions, an Analysis Population refers to a particular set of participants and an Analysis Set defines the time contributed to analyses by participants in a given Population. Additional censoring rules for analyses based on these sets are described in relevant sections.

A. Treated Population

The Treated Population consists of all enrolled participants who receive a dose of study drug. Unless noted otherwise, all analyses based on this population will be performed per intention-to-treat principles, ignoring any randomization errors, allocation errors, or the receipt of injections during follow-up that differ from the baseline injection site.

i. Safety Analysis Set

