The Safety Analysis Set includes all follow up time contributed by each participant in the Treated Population, including time in the 8-28 day 'late' period for reinjections or final visits.

ii. Treated Analysis Set

The Treated Analysis Set includes follow up time contributed by each participant in the Treated Population and censors time in analysis for each woman at the earlier of the following: her estimated date of fertilization (EDF) (for women becoming pregnant), her last negative urine pregnancy test (for women who do not become pregnant), and the date that is 7 days after her last target visit date. In addition, The Treated Analysis Set excludes any follow-up time contributed by a woman when she was 8 to 28 days late for a re-injection.

For example, a woman who returns on week 20 rather than week 17 for her month 4 re-injection (i.e., 2 weeks past her 7-day grace period) but who returns precisely at 18-week intervals for her month 8 and final visit without becoming pregnant, would contribute 56 (20 + 18 +18) weeks to the Safety Analysis Set but only 54 (18 + 18 +18) weeks to the Treated Analysis Set.

iii. Perfect use Analysis Set

The Perfect Use Analysis Set is a subset of the Treated Analysis Set, excluding any time during which a participant reported using another contraceptive method (including condoms) or drugs known to impact ovarian function or PK of MPA, unless she became pregnant in that period and the drug being used is known to only *increase* the risk of pregnancy among women using injectable DMPA. Exclusionary periods for prohibited drugs or contraceptive methods other than condoms will be determined based on the start and end dates provided on the corresponding concomitant medication form. If the end date is missing or indicated as ongoing, then all follow-up time after the reported start date will be excluded. Periods of exclusion for condom use will be determined based on a question with three options recorded on the FU CRF at each visit. If a participant reports using condoms in the last 4 weeks and at any other time since the last injection, then all time since the previous injection date will be excluded; if a participant reports using condoms since last injection but not in the last 4 weeks, then only the time between the previous injection date and the date which is 4 weeks prior to the report visit will be excluded; and if a participant

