The primary analysis of efficacy will be based on the pregnancy Pearl Index, defined as the number of pregnancies that occur during the treatment period per 100 women-years of time contributed to the Treated Analysis Set among women randomized to receive injections in the abdomen or thigh. Participants who do not become pregnant or who have EDFs that fall outside the windows used to define primary outcomes will be censored on the date of last negative urine pregnancy test or the end of the plus 7-day grace period since last injection, whichever is earlier. An exact 95% confidence interval for the Pearl Index will be computed based on an assumption that the number of pregnancies occurring in the treatment period follows a Poisson distribution. A listing of all participants who become pregnant during the study will include at least study center, randomized injection site, days on treatment until EDF, inclusion in the primary efficacy analysis, and pregnancy outcome.

C. Secondary Efficacy Analysis

Secondary efficacy analyses will include:

- Typical use life-table estimates of the cumulative probability of pregnancy through 3 treatment cycles, based on the Treated Population and Safety Analysis Set (excluding women randomized to receive injections in the upper arm). Point-wise 95% confidence intervals will be computed using the log-log transformation. For this analysis, the first, second and third treatment cycle can be up to 21, 22, and 22 weeks long, respectively (after accounting for up to a 28-day late period for re-injections or final study visit).
- An estimate of the Pearl Index computed based on the Perfect Use Analysis Set (excluding participants randomized to receive injections in the upper arm).
- An estimate of the Pearl Index based on the Treated Population and Safety Analysis Set (excluding participants randomized to receive injections in the upper arm). This estimate will include all follow-up time contributed (regardless of pregnancy status) and any pregnancies detected while participants are up to 28 days late for their visits.
- An estimate of the Pearl Index computed per the primary analysis, but including women randomized to receive injections in the upper arm.

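### The SAP's late-inclusive Pearl Index counts pregnancies by detection instead of EDF and leaves exposure uncensored, so as written it is biased modestly low; the life table on the same set lacks last-negative-test censoring

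*SAP*

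**What the plan says.** **Late-inclusive Pearl Index, numerator.** Protocol 10.6.2.2 specifies a "Pearl Index that includes any pregnancies with EDF that fall in an 8-28 day" late period for re-injections or final visits. SAP IX.C instead counts "any pregnancies detected while participants are up to 28 days late for their visits".

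**Late-inclusive Pearl Index, denominator.** The SAP states: "This estimate will include all follow-up time contributed (regardless of pregnancy status"). The protocol has a similar clause but attaches it only to person-time in the late periods.

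**The set used.** "The Safety Analysis Set includes all follow up time contributed by each participant in the Treated Population" (SAP V.A.i). The Treated Analysis Set (V.A.ii), by contrast, stops at the earliest of EDF, "her last negative urine pregnancy test (for women who do not become pregnant"), and 7 days after the last target visit. SAP V says: "Additional censoring rules for analyses based on these sets are described in relevant sections". IX.C adds no rule on EDF or last negative test.

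**Typical-use life table.** It is "based on the Treated Population and Safety Analysis Set (excluding women randomized to receive injections in the upper arm"). Its only time limit is that "the first, second and third treatment cycle can be up to 21, 22, and 22 weeks long, respectively". It has no detection wording and no stated event date.

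**Related protocol rules.** Sections 3.3 and 10.6.1 date time to pregnancy at EDF. Section 3.3 censors non-pregnant women no later than the last negative test. Sections 3.14.9 and 6 provide for assessing EDF in women who report pregnancy within 3 months of exit, and section 6 puts those with EDF in the treatment period into the primary assessment. Section 3.14.3.2 has no routine pregnancy test at month 8.

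**The concern.** The protocol includes pregnancies by when conception occurred. For this index the SAP includes them by when they were found. The SAP gives no reason, although Protocol 10.13 says that deviations will be reported with their reasons. A woman who conceives shortly before her final visit, tests negative there and reports the pregnancy a month later has an EDF inside the window but was not detected inside it. If that EDF is also in the treatment period, the primary index counts her and the supposedly more inclusive index does not.

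The denominator has a separate problem. A woman who attends month 8 without a test and is then lost adds the whole interval since month 4 as event-free exposure, although no test covers it. Time between conception and discovery of a pregnancy also counts. The late-inclusive index and the typical-use life table are the pregnancy estimates that keep late time, so a reader will use them to judge how the regimen performs when women return late.

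**Working it through.** **1. The plan's own figures.** SAP V.A.ii's example reproduces: 20 + 18 + 18 = 56 weeks in the Safety Analysis Set and 18 + 18 + 18 = 54 in the Treated Analysis Set. The life-table caps reproduce: 17 + 4 = 21 weeks and 18 + 4 = 22 weeks. The sets differ as described for late time; the example does not involve EDF or last-negative censoring.

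**2. Direction for the Pearl Index.**
- Any pregnancy detected by 28 days late has an earlier EDF, so EDF counting includes it. The reverse is not true, so the numerator can only shrink.
- Dropping the EDF and last-negative stops can only add time, so the denominator can only grow.

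**3. Baseline exposure.** 710 women with 80% completing (SAP III.A), non-completers assumed to give half a year each: 568 + 142 × 0.5 = 639 woman-years (WY).

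**4. Post-conception time.** Five pregnancies with 126 to 252 extra days each (assumed) add 5 × 126/365.25 = 1.7 to 5 × 252/365.25 = 3.4 WY. The index goes from 500/639 = 0.782 to 0.780-0.778, a fall of 0.3-0.5%.

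**5. Untested time.** A woman lost after an untested month 8 visit adds 245 − 119 = 126 days. For an assumed share *s* of 710 women, added WY = 710 × *s* × 126/365.25, and the index is multiplied by 639/(639 + added WY).

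| *s* | Added WY | 0.75 becomes | Relative fall |
|---|---|---|---|
| 5% | 12.2 | 0.736 | 1.9% |
| 10% | 24.5 | 0.722 | 3.7% |
| 20% | 49.0 | 0.697 | 7.1% |

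The 20% row puts all non-completion after an untested month 8 visit and is the widest bound.

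**6. All effects together.** A simulation (710 women, 1,500 replicates per scenario) compared the literal SAP rule with EDF counting plus last-negative censoring, late time kept in both. Assumed inputs, not from the documents: 10% of visits 8-28 days late; 14 days from fertilization to a positive test; half of dropouts tested at exit; 0.5 or 1.0 pregnancies per 100 WY; late-period hazard 1 or 5 times baseline; dropout 10% or 20%; all post-exit pregnancies of completers reported. The literal index was 0.945 to 0.961 of the EDF-based one, for example 0.505 to 0.481 and 1.029 to 0.973.

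A hand check agrees. 568 completers × 14/365.25 = 21.8 WY, in which a conception is too recent to show at the final visit. At 0.5 per 100 WY this is 0.11 pregnancies, or 3.2% of the 3.38 expected in the matching scenario. Exposure there rises from 669 to 676 WY, about 1%. Together this is about 4%, mostly from the numerator.

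**7. Life table.** A woman leaves the risk set at her event, so with EDF dating no post-conception time enters. Untested time remains. If a share *s* is lost after an untested month 8 visit, with no earlier loss and equal risk per cycle (assumed), cycle 2 risk is understated by *s* and three-cycle risk by about *s*/3: 1.7% at 5% and 6.7% at 20%.

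**The case against.** **Scale and role.** The primary index keeps both EDF and last-negative censoring, and no decision rule in the documents rests on these secondary estimates. Four events in 639 WY give 0.626 with an exact upper bound of 1.603, so a 4-7% shift is well inside the sampling error. This stands.

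**Wording.** The detection clause may be meant to add late-period pregnancies to those already in the primary index. Then only late-window conceptions found after exit are lost. With 10% of 568 completers 21 days late, exposure is 57 × 21/365.25 = 3.3 WY: 0.03 pregnancies at 1 per 100 WY and 0.16 at five times that, even if all are missed. The SAP does not say this, but the 4-6% figure does rest on the literal reading. The clause on pregnancy status also comes from the protocol, and may mean only that late time counts for every woman.

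**Testing.** Final-visit procedures, with a urine test, are to be done at early discontinuation where possible (Protocol 3.12.2, 3.14.3.3). At month 8, women more than 7 days late and the planned 139 body-composition participants are tested. The 20% row is therefore a bound, not an expectation.

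**Stronger readings that a reader might infer.**
- That both analyses count by detection and are diluted by post-conception time. The detection wording is only in the Pearl Index bullet, and the protocol dates time to pregnancy at EDF, so neither effect carries to the life table.
- That up to all late-window conceptions are missed. With a 10-21 day test lag (assumed), (21 − 10)/21 = 52% down to (21 − 21)/21 = 0% would be detectable by day 28 late. But a woman who is re-injected stays in follow-up and can be found pregnant later. The loss arises mainly at final or exit visits.
- That the index determines the grace period. It pools all follow-up, and Protocol 3.2 ties the grace period to trough concentrations and half-life.

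**Conclusion.** The mismatch between detection and EDF, and the absence of EDF and last-negative stops, are both in the current text. As written, the late-inclusive Pearl Index can be biased only downward relative to EDF counting with last-negative censoring. The size is about 4-6% relative under the simulated assumptions and the literal reading, and up to about 7% at the widest denominator bound. For the typical-use life table the supported point is narrower: untested time inflates the risk set modestly, and the SAP leaves the event date open. If detection dates were used there, some third-cycle conceptions could fall past the 22-week cap.

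The correction is worth making despite the small average effect. Events are few: at 639 WY, losing one of five pregnancies moves the index from 0.782 to 0.626. An index presented as more inclusive than the primary should not be able to omit a pregnancy that the primary counts.

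**What to change.** In SAP IX.C, for both the late-inclusive Pearl Index and the typical-use life table:

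- Include and date pregnancies by EDF, through 28 days past the target visit date. This agrees with the 21/22/22-week caps (119 + 28 = 147 days; 126 + 28 = 154 days).
- Stop efficacy time at the earliest of EDF, last negative pregnancy test (for women who do not become pregnant), and 28 days past target, keeping the late periods.
- Reconcile this with Protocol 10.6.2.2, which counts late-period person-time whatever the pregnancy status. Either state that the clause means only that late time is kept for all women, or record the departure and its reason under Protocol 10.13.
- Keep the uncensored Safety Analysis Set for safety, and give the late-inclusive efficacy set its own name.

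The cost is SAP wording and slightly less favourable secondary estimates. No new data are needed, and the primary analysis does not change.

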10.1 Sample Size and Power Considerations

The sample size of 710 women receiving injections in the abdomen or thigh is expected to be sufficient to ensure that the difference between the estimated Pearl Index and the corresponding upper 95%

confidence bound does not exceed 1.0, so long as the observed index is less than 0.75 and at least 80% of participants complete 12 months of follow-up. In addition, a cohort of 120 women (40 per SC injection site) is sufficient to provide 85% power to detect 30% relative differences in PK parameters between injection sites, assuming the corresponding coefficient of variation is no more than 40% and using two-sided 0.05 significance tests.

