Treatment will begin in the first 5 days of menses. A single MPA serum sample will be collected from all participants at baseline. All participants will be scheduled to receive re-injections at month 4 (approximately 17 weeks after treatment initiation) and month 8 (approximately 35 weeks after treatment initiation) and complete their planned follow-up at month 12 (approximately 53 weeks after treatment initiation). There will be a plus 7-day grace period for re-injections, but women who are up to 28 days late may continue treatment if they have a negative urine pregnancy test. Urine pregnancy testing will be performed at month 4, at study exit, at month 8 if the participant is more than 7 days late for her visit, and at any time during the study if clinically indicated. Participants will be evaluated for injection site reactions and asked to provide information on adverse events, prohibited concomitant medications and other contraceptive use, vaginal bleeding, and method acceptability at months 4, 8 and 12. Information on adverse events and use of any prohibited concomitant medications will be recorded if reported by participants at month 2 and 3 PK visits and at any unscheduled visits.

III. General Analytic Considerations

A. Study Size and Power

The sample size of 710 women receiving injections in the abdomen or upper thigh is expected to be sufficient to ensure that the difference between the estimated Pearl Index (pregnancies per 100 woman-years of use) and the corresponding upper 95% confidence bound does not exceed 1.0, so long as the observed Pearl Index is less than 0.75 and at least 80% of participants complete 12 months of follow-up. (The study has a 90% chance of achieving this precision target if the true (unobserved) pregnancy rate is no more than 0.5 per 100 women-years). In

addition, a cohort of 120 women (40 receiving injections in each the abdomen, upper thigh, and back of the upper arm) is sufficient to provide 85% power to detect 30% relative differences in PK parameters between injection sites, assuming the coefficient of variation is no more than 40% and using two-sided 0.05 level significance tests.

B. Data Source

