All participants will receive the same study drug, Sayana® Press, and will be randomized to receive their injections in one of three subcutaneous injection sites: abdomen, upper thigh, or back of the upper arm. One cohort of N=630 will be randomized 1:1 to receive their subcutaneous injections of Sayana® Press in the abdomen or upper thigh, and a second PK cohort of N=120 women who agree to serum MPA testing at 6 time points (baseline and

months 2, 3, 4, 8, and 12) will be randomized 1:1:1 to receive their injections in the abdomen, upper thigh, or back of the upper arm. Using this randomization scheme, 355 women will receive their injections in the abdomen, 355 in the upper thigh, and 40 in the back of the upper arm. Randomization in each cohort will use randomly-permuted blocks, stratified by study center and cohort with the following planned enrollment totals at each site: 250 at the center in Brazil (UNICAMP), 150 at the center in Chile (ICMER), and 350 at the center in the Dominican Republic (Profamilia). Within these totals, 42 at Profamilia, 36 at ICMER, and 42 at UNICAMP will be randomized in the PK cohort and the remainder of the enrollment total at each center will be randomized in the primary cohort. Randomization sequences will be created for each combination of study center and cohort by an FHI 360 Randomization Statistician using a validated program written in SAS® version 9.4 or higher. Recognizing that actual numbers of participants enrolled at each site may change during the enrollment period due to center performance or other issues, additional randomization numbers will be generated for the primary cohort within each center to allow one or two centers to expand enrollment to compensate for reduced enrollment at the remaining center(s)².

B. Allocation Concealment

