Serum MPA concentrations that fall within defined sampling windows (see Appendix A) will be summarized by timepoint and injection site in the following ways: 1) graphically using box plots with whiskers extending to 5th and 95th percentiles, and 2) in tables using means, geometric means, quartiles, minima, maxima, standard deviations, and percent coefficients of variation. A listing of all MPA concentrations for each participant will be provided along with an indication of any that fall outside of defined sampling windows, or any excluded from the PK Analysis Set due to concomitant medication use, injection in an anatomical site different from the site used at enrollment, or insertion of multiple Sayana Press units at the time of injection. The listing will also include subject age and BMI at time of sampling.

Month 2, 3, and 4 data will be used to estimate the apparent half-life for each injection site based on mixed-effects log-linear models with random intercept and slope terms, under the assumption that the terminal phase of absorption begins by month 2.⁵ Unique variance components will be used for each injection site, and observations falling outside sampling windows will not be excluded. The estimated slope (*m*) for each injection site will be used to calculate the apparent half-life according to the following formula: $half-life = \ln(2)/(-m)$. Pharmacokinetics in the terminal phase will be compared across injection sites based on overall and, if significant at the 0.05 level, pairwise Wald-type tests of differences in fixed-effects intercepts and slopes. Differences in variance components (both within-and between-subject effects) will similarly be assessed using likelihood ratio-tests.

Accumulation of MPA concentrations at months 8 and 12 will be estimated for each injection site by calculating the geometric mean ratio (GMR) of trough concentrations at 8 or 12 months to the trough concentration at 4 months, using mixed-effects models to compute 95% CIs of each GMR (with unspecified covariance of log-transformed repeated measures). Any MPA concentrations that are measured more than 7 days past a participant's scheduled injection date (along with any future measurements) will be excluded from the above accumulation

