⁵ This assumption will be formally assessed using appropriate log-linear random-effects model diagnostics, and by comparing predicted month 8 and month 12 concentrations (based on the half-life estimates and 4-month data) with the observed month 8 and 12 concentrations.

analysis. Steady-state accumulation ratios will be estimated as $R = [1 - (0.5)^{\text{dosing interval/half-life}}]^{-1}$, where the dosing interval is assumed to be 126 days and the half-life is estimated in the method described above.

The effects of study center, BMI, and age on trough concentrations will be explored graphically and by incorporating covariates in mixed-effects models based on month 4, 8, and 12 data. Intra-subject variability across injection cycles may also be explored using MPA trough levels at months 4, 8, and 12.

B. Safety

Safety endpoints will include serious adverse events (SAEs), adverse events (AEs) leading to product withdrawal, injection site reactions, bleeding patterns, blood pressure, and body weight recorded at months 4, 8, and final visits. All SAEs, AEs leading to product withdrawal, and AEs which are Grade 1 or higher ISRs will be coded by a trained medical coder at FHI 360 using the Medical Dictionary for Regulatory Activities (MedDRA) to classify them according to preferred term and system organ class (SOC). Safety analyses will be performed using the Treated Population and Safety Analysis Set and will be based on treatment group actually received.

All relevant information on any SAEs will be discussed in the subject narrative included in any clinical study report and in a listing. Numbers and percentages of participants experiencing AEs (specifically AEs leading to product withdrawal and ISRs which are Grade 1 or higher) will be presented by severity, study center, and injection site. Percentages of participants experiencing specified AEs will be compared across injection sites (pooled over severity and study center) within each SOC using Fisher's exact tests. Listings of any AEs will include actual injection site, a description of AE, type of AE, days to onset, relatedness to Sayana Press, seriousness, severity, outcome, and duration. Numbers and percentages of participants experiencing ISRs of any grade will be summarized by injection site, and ISRs will also be presented in a listing.

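### SAP X.A compares injection sites on MPA levels without study center (a randomization stratum) or baseline BMI; prespecifying both could tighten the level and trough contrasts at almost no cost

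*SAP*

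**What the plan says.** SAP IV.A: "Randomization in each cohort will use randomly-permuted blocks, stratified by study center and cohort". The PK cohort is planned as 42, 36 and 42 women at the three centers, allocated 1:1:1 to abdomen, thigh and upper arm. Protocol 3.14.2 has height and weight recorded at enrollment, so baseline BMI can be derived.

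SAP X.A fits a log-linear mixed model to the month 2, 3 and 4 concentrations. It has random intercepts and slopes and separate variance components for each injection site. Then: "Pharmacokinetics in the terminal phase will be compared across injection sites based on overall and, if significant at the 0.05 level, pairwise Wald-type tests"; the tests concern fixed-effect intercepts and slopes. No center or BMI term is named.

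The covariates come later in the same section: "The effects of study center, BMI, and age on trough concentrations will be explored graphically and by incorporating covariates in mixed-effects models", using months 4, 8 and 12. SAP III.D names center adjustment for the primary efficacy analysis and refers other adjustments to their own sections.

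Protocol 10.7.2 compares injection sites through 95% confidence intervals for geometric mean ratios of half-life and trough. It also plans an exploratory analysis of covariance. SAP X.A does not say which model supplies the between-site trough ratios.

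**The concern.** When randomization is stratified by center, the injection-site groups are balanced on center by design. An analysis that omits center leaves any between-center variation in the error term, so the standard error is too large whenever centers differ. Omitting a prognostic baseline covariate such as BMI likewise leaves explainable variance in the error.

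The SAP already follows this principle elsewhere: in SAP IX.C the comparison of pregnancy risk between injection sites is a log-rank test stratified on center. The PK comparison of women randomized under the same scheme is not.

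What is at stake is precision on a named secondary objective with 40 women per injection site. There is also a matter of prespecification. The SAP allows a trough model with center and BMI but does not say whether adjusted or unadjusted contrasts are the main result, so that choice could be made after both have been seen.

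**Working it through.** **Inputs (SAP III.A, repeated in Protocol 10.1).**
- Claim: the PK cohort "is sufficient to provide 85% power to detect 30% relative differences in PK parameters between injection sites".
- Size: 120 women in all, 40 at each of three injection sites.
- Variability: a CV of at most 40%.
- Test level: 0.05, two-sided.
- The share of variance explained by center and BMI (R²) is not given. It is assumed here to lie between 0 and 0.30.

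**Step 1: reproduce the stated power.**
- Log-scale SD = √ln(1 + 0.4²) = 0.385.
- Difference = ln(1.30) = 0.262.
- Standard error of a two-site contrast = 0.385 × √(2/40) = 0.0861.
- Power is 86.1% by the normal approximation and 85.3% by a two-sample t test (78 df). Both agree with the stated 85%, with no covariates.

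**Step 2: unadjusted interval.** With three sites and 120 women there are 117 residual df. The log-scale half-width is 1.980 × 0.0861 = 0.171, so the 95% interval for a geometric mean ratio is the estimate multiplied and divided by e^0.171 = 1.186.

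**Step 3: add center (2 df) and BMI (1 df).** The residual SD becomes 0.385 × √(1 − R²) with 114 df. A factor √(1 + 1/114) allows for chance imbalance in BMI. Half-width = 1.981 × 0.0861 × √(1 − R²) × √(1 + 1/114).

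| R² (share of total log variance, assumed) | Interval factor | Change in half-width | Power for ratio 1.30 |
|---|---|---|---|
| 0 | 1.187 | +0.5% | 85% |
| 0.10 | 1.177 | -4.7% | 89% |
| 0.20 | 1.166 | -10.1% | 92% |
| 0.30 | 1.154 | -15.9% | 95% |

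Unadjusted power on the same footing (117 df) is 85.6%. Break-even is at about R² = 0.009.

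**Step 4: total or between-woman variance.** The 0.385 contains within-woman variation, which center and baseline BMI cannot explain. If, for illustration, 30% of the variance is within-woman, then 20% of the between-woman part is 0.20 × 0.70 = 0.14 of the total. The standard error falls by 1 − √0.86 = 7%, against 1 − √0.80 = 11% when 20% of the total is explained.

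**Step 5: slopes.** In 60 simulated PK trials (120 women, days 61, 91 and 119, 14/12/14 per injection site by center, BMI explaining 20% of intercept variance), adding center and BMI as main effects left the slope standard error unchanged (ratio 1.000). The standard error of the level difference at month 3 fell by about 10%. The simulation assumed complete, on-schedule samples and common variance components, so under the SAP's site-specific components the slope result is approximate.

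**The case against.** The strongest reply is that nothing is wrong as planned. Randomization protects the unadjusted contrast from bias, leaving out a prognostic stratum errs on the conservative side, and the design reaches its power target unadjusted. All of that stands. A reader might infer that the comparison is biased, invalid or short of its stated power; the documents support none of these.

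Second, covariates are not ignored: SAP X.A puts center, BMI and age into the trough models. That is correct. The gap is only that this work is exploratory and is not named as the source of the injection-site contrast.

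Third, the sentence on Wald-type tests specifies no intervals, and the only 95% intervals in SAP X.A are for month 8 or 12 against month 4 within an injection site, where baseline main effects should do little. This stands for those accumulation ratios. The between-site intervals are in Protocol 10.7.2, and the same standard error drives tests and intervals.

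Fourth, a reader might want the covariates in every PK model, with time interactions. That goes too far. Protocol 3.2 includes the upper-arm group partly to see whether concentrations vary more at that site, and adjustment would change that comparison to residual variability. Covariate-by-time terms would leave no single slope per injection site for the half-life formula, and that half-life feeds the steady-state accumulation ratio.

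**Conclusion.** The point holds as a modest, nearly free gain in precision on a secondary objective, and as a request to name the main model. It applies to between-site contrasts of terminal-phase level and of trough.

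Its size depends on an R² that the documents do not give: from +0.5% in interval half-width if center and BMI explain nothing to about -16% if they explain 30% of total log-scale variance. These figures rest on the plan's own assumptions of a 40% CV and 40 evaluable women per site, and they shrink if the share refers to between-woman variance. It would be tempting to say outright that the planned intervals are too wide; that is true only if center or BMI is prognostic. No gain should be claimed for half-life from main effects.

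**What to change.** In SAP X.A, prespecify study center and enrollment BMI as fixed main effects in the models that give the between-site contrasts of:

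- terminal-phase level, with time centered so that the intercept is a concentration within the sampled period; and
- month 4, 8 and 12 troughs, reported as the geometric mean ratios with 95% confidence intervals promised in Protocol 10.7.2.

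State that the adjusted contrasts are the main result and the unadjusted ones supportive. Keep the half-life (slope), steady-state accumulation and variance-component comparisons on the model as now written.

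The cost is about 3 degrees of freedom, a short addition to the SAP and a little more analysis work. No new data are needed.
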